13.2 Sample Size/Accrual Rate

Approximately 82 patients with unresectable cholangiocarcinoma will be enrolled in this randomized phase 2 trial with the goal of accruing at least 76 evaluable subjects, with progression free survival (PFS) as the primary endpoint. We plan to enroll approximately 6 patients per month across the multiple trial sites, and because of the rapid progression of the disease, expect little or no censoring. We anticipate fully enrolling this trial within 18 months, permitting an average of 12 months of follow up, and completing the study within 3 years. This design yields 90% power at a one-sided type I error rate of 5% assuming a difference in median PFS between the arms of 2 months (2 months vs. 4 months), and assuming that 71 events will have occurred among 76 patients over the study period. Calculations were performed without stratification, as it is not known whether outcome varies by site.

Patients with tumor that is safely accessible for biopsy will obtain a biopsy at study baseline and a repeat on-treatment biopsy at treatment day 21. Based on previous clinical experience, we anticipate that paired biopsy samples will be successfully obtained in at least 50% of participants. We anticipate obtaining approximately 20 subjects in each treatment arm with paired samples available for analysis, offering 80% power for detecting an increase in CD8+ density equal to 0.8s.d., using a one-sided t-test with alpha=0.05, and more than 90% power for detecting an effect size of 1.0s.d.

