11. MEASUREMENT OF EFFECT

11.1 Antitumor Effect – Solid Tumors

For the purposes of this study, patients should be re-evaluated for response every 8 weeks. Response and progression will be evaluated in this study using the new international criteria proposed by the revised Response Evaluation Criteria in Solid Tumors (RECIST) guideline (version 1.1) (Eisenhauer *et al.*, 2009). Changes in the largest diameter (unidimensional measurement) of the tumor lesions and the shortest diameter in the case of malignant lymph nodes are used in the RECIST criteria.

This study will [also] evaluate response and progression using immune-related response criteria (irRC) (Wolchok *et al.*, 2009). See **Appendix D** for a detailed description of the evaluation criteria.

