13. STATISTICAL CONSIDERATIONS

13.1 Study Design/Endpoints

The proposed study is an open-label, randomized phase 2 multicenter trial evaluating cobimetinib in combination with atezolizumab compared with atezolizumab monotherapy in unresectable cholangiocarcinoma.

The primary clinical endpoint is progression free survival and the primary objective of the trial is to determine whether the combination of cobimetinib in combination with atezolizumab yields a clinically compelling antitumor activity measured as progression free survival (PFS). Additional secondary endpoints include safety, objective response rate (ORR, assessed by RECIST 1.1), overall survival (OS), and other immunologic correlates.

The principle correlative objective of the trial is to determine whether the combination of cobimetinib and atezolizumab increases immune response compared to atezolizumab monotherapy. The change CD8+ density within tumor after 21 days of treatment, as compared to baseline, is an integrated biomarker for this clinical trial.

The study is planned with 76 evaluable subjects (38 subjects per treatment arm), to achieve 90% power using a 1-sided test with alpha=0.05. Both of these drugs are in common use and will be given at full dose. The combination of cobimetinib and atezolizumab was previously tested, and well tolerated in a similar population of patients with metastatic colorectal cancer, so unacceptable rates of toxicity are not expected, but the present study will be continuously monitored for adverse events. The primary study team made up of the study PI [name], [REDACTED] Dr. [REDACTED], and lead study nurse and coordinator at the lead site Johns Hopkins will meet weekly to discuss adverse events. In addition, the primary study team will have bimonthly calls with representatives at all the enrolling sites to monitor toxicity continuously.

Progression-free survival is defined as the duration of time from date of randomization to time of progression or death. The evaluable population includes all subjects who have completed at least one dose of therapy and have received at least one follow-up scan. Patients who come off of study treatment for clinical progression prior to the first follow-up scan (i.e. clinical progression)

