will also be considered evaluable and will be coded as progressors for the analysis. Due to the rapid progression of the disease in the majority of patients, little loss to follow up is expected, but subjects who are lost to follow-up as of the data analysis cutoff date will be right-censored. The censoring date will be determined from the date the subject was last evaluated for progression. PFS within each treatment arm will be summarized descriptively using Kaplan-Meier plots, and compared between groups, under the assumption of Cox proportional hazards, using the stratified log-rank test to account for tumor site. An interim analysis will be conducted when half the required PFS events have been observed (35). The trial will be stopped early for futility if the p-value from the log-rank statistic is greater than 0.5 (i.e., the PFS is worse for study arm B than for study arm A).

The analysis will be stratified on site of disease (gallbladder cancer, intrahepatic cholangiocarcinoma, and extrahepatic cholangiocarcinoma). An interim analysis will be conducted when half the required PFS events have been seen (35), and the trial will be stopped early for futility if median PFS is lower by any amount, under the combination therapy than under monotherapy.

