13.3 Stratification Factors

After the screening phase, eligible subjects will be stratified according to the site of disease: 1) gallbladder cancer (GBC); 2) intrahepatic (IHC); and 3) extrahepatic cholangiocarcinoma (EHC). There will be no further stratification based on other patient or tumor characteristics (such as age, sex) in this trial. Sample size calculations were performed without stratification, as it is not known whether outcome varies by site.

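### The stated 90% power belongs to a fixed, unstratified test; the planned stratified log-rank test with its futility look has about 86-87% at 71 events

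*Combined protocol and SAP*

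**What the plan says.** Section 13.1 plans 76 evaluable subjects, 38 per arm, "to achieve 90% power using a 1-sided test with alpha=0.05". Section 13.2 repeats the 90% ("This design yields 90% power at a one-sided type I error rate of 5" per cent), for medians of 2 and 4 months and "assuming that 71 events will have occurred among 76 patients over the study period".

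The primary comparison of PFS in 13.1 is made "using the stratified log-rank test to account for tumor site". The strata are gallbladder, intrahepatic and extrahepatic disease. An interim analysis follows at 35 PFS events: "The trial will be stopped early for futility if the p-value from the log-rank statistic is greater than 0.5". The next paragraph of 13.1 words the rule differently. There, the trial stops if the combination has the shorter median PFS, however small the gap.

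On the basis of the calculation, 13.3 says "Sample size calculations were performed without stratification", because it is not known whether outcome differs by site. Section 13.2 says the same. Neither section says how much power the stratified test or the futility look costs.

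**The concern.** The power figure and the primary analysis describe different tests. The reason given for leaving out stratification is that site may not be prognostic, but that does not remove the loss. In a sample of 76 split over three strata, some risk sets within a stratum contain patients from one arm only and add nothing to the log-rank statistic. The stratified test therefore loses some power even when outcome is the same at every site. The futility look can only lower power further, because some trials with a real effect will be stopped.

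At stake is how a negative result is read. A reader who takes the plan at its word would believe that a doubling of median PFS is missed one time in ten.

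**Working it through.** **Inputs from the plan.** One-sided alpha 0.05 and 38 patients per arm (13.1); medians 2 and 4 months, so HR = 0.5 under exponential PFS (13.2); 71 events in 76 patients and 6 patients accrued per month (13.2); three strata and a look at 35 events (13.1).

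**Step 1: reproduce the 90%.** Schoenfeld's formula with 1:1 allocation:

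power = Φ(½·√D·|ln HR| − 1.645) = Φ(½ × 8.426 × 0.693 − 1.645) = Φ(1.275) = 0.899.

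The plan's figure is right for a fixed, unstratified test. Freedman's formula, Φ(√71/3 − 1.645) = Φ(1.164), gives 0.878, so the choice of approximation already matters at HR 0.5.

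**Step 2: the look alone, large-sample.** The interim drift is ½ × √35 × 0.693 = 2.05, so the chance of stopping under HR 0.5 is Φ(−2.05) = 2.0%. The joint probability of passing the look and rejecting at 71 events (correlation √(35/71) = 0.70) is 0.893. The cost is 0.899 − 0.893, about 0.6 points.

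**Step 3: simulate the planned analysis.** Exponential PFS, HR 0.5, 76 patients, final test at 71 events against 1.645, look at 35 events with a stop if one-sided p > 0.5. Assumptions not in the documents are the site mix, randomisation balanced within strata, and use of the stratified statistic at the look. There were 30,000 trials per row (standard error about 0.2 points).

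| Assumed site mix (%) | Unstratified, no look | Stratified, no look | Stratified, p > 0.5 look | Stratified, median rule |
|---|---|---|---|---|
| equal thirds | 88.9 | 87.1 | 86.4 | 84.7 |
| 20/55/25 | 88.7 | 87.2 | 86.5 | 84.5 |
| 30/50/20 | 88.7 | 86.9 | 86.2 | 84.5 |
| 10/80/10 | 89.1 | 87.5 | 86.9 | 85.1 |

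**Step 4: split the shortfall.**
- Approximation: 89.9% to about 89%, about 1 point.
- Stratifying a small sample: 1.5-2 points (for 20/55/25, 88.7 − 87.2 = 1.5).
- The p > 0.5 look: 0.6-0.7 points.
- Total: 89.9 − 86.9 = 3.0 to 89.9 − 86.2 = 3.7 points.

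**Step 5: sensitivity.**
- Without balance within strata: 85.4-85.6%.
- Site prognostic (hazard multipliers 1.5/1/0.7, mix 20/55/25), with the look: 86.2% stratified against 86.0% unstratified. Dropping the strata is therefore not a remedy.
- Type I error of the stratified test with the look: 0.0497.
- Every event moved to an 8-week scan grid: separate sets of runs disagree on direction (86.4% to 86.0% in one, 86.3-86.4% to 87.4% in another).
- Median rule: about 5% false stops at HR 0.5 when events are seen in continuous time. On the scan grid this falls to about 1%, and power is 86.2%.
- More events, with the p > 0.5 look: 87.7% at 75 of 76, 88.5% at 77 of 82, and 89.1% with about 82 events in 82 patients.

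**The case against.** The strongest reply is that nothing was miscalculated or hidden. The 90% follows from the stated inputs, and the plan says twice that stratification was left out. Sizing with the unstratified formula and testing with the stratified statistic is common practice. This stands: a reader might infer an arithmetic error, and there is none. What the disclosure lacks is the size of the loss and any mention of the look.

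A second reply is that 71 events is a planning assumption. The plan expects about 82 enrolled and little censoring, so more events are likely and power could reach 88-89%. This also stands, but the 90% is tied to 71 events in 76, and even the more favourable cases stay below it.

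A third is that the gap is small beside the uncertainty in the effect. By the Schoenfeld formula, a combination median of 3.8 months instead of 4 gives 85.5%, and 4.2 gives 93.1%. That is true, and it limits the importance of the point. It does not make the stated figure the power of the planned test.

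A reader might also infer a larger shortfall, down to 85%, from the 8-weekly assessments in 11.1 ("patients should be re-evaluated for response every 8 weeks"). The documents do not support treating progression as seen only on that grid: 13.1 counts clinical progression before the first scan, and death is an event. The simulations show no consistent loss from the grid.

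**Conclusion.** The point holds as a mismatch between the calculation and the planned analysis. At 71 events in 76 patients, with medians of 2 and 4 months, the stratified log-rank test with the p > 0.5 look has about 86-87% power, 3-4 points under the stated 90%. The type II error is about 13-14%. Type I error is not affected.

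The result rests on finite-sample simulation, proportional hazards with exponential PFS, an assumed site mix and randomisation balanced within strata. It is stable over the mixes tried and about a point lower without that balance. It also depends on which futility rule applies: under the median rule the corresponding figure is about 84-85% in continuous time.

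The documents do not support the inference that the trial is seriously underpowered or needs more patients. The shortfall is modest and narrows if follow-up yields more than 71 events.

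**What to change.** First reconcile the two futility rules in 13.1 (log-rank p > 0.5, or a lower median PFS on the combination), since the power depends on which one governs, and say whether the look uses the stratified statistic.

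Then restate power in 13.1 and 13.2 as about 86-87% for the stratified log-rank test at 71 events with the p > 0.5 look, or give the matching figure if the median rule is kept. State the assumed site mix. The 90% may remain if it is labelled as the fixed, unstratified large-sample value. The plan may add that following patients to more events (about 76 of 76, or 77-82 of 82) gives about 88-89%.

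The cost is one slightly less favourable figure. No extra patients are needed and conduct does not change.

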13.3 Stratification Factors

After the screening phase, eligible subjects will be stratified according to the site of disease: 1) gallbladder cancer (GBC); 2) intrahepatic (IHC); and 3) extrahepatic cholangiocarcinoma (EHC). There will be no further stratification based on other patient or tumor characteristics (such as age, sex) in this trial. Sample size calculations were performed without stratification, as it is not known whether outcome varies by site.

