13.4 Analysis of Secondary Endpoints

Overall survival is defined as the duration of time from date of randomization to time of death. Subjects lost to follow-up or whose vital status is unknown, will be right-censored at the date the subject was last known to be alive. Every effort will be made to determine outcome, including phone calls, certified mail, and the checking of public records as necessary. The evaluable population is as defined for the primary endpoint. Results will be summarized descriptively using Kaplan-Meier plots, and compared between groups, under the assumption of proportional hazards, using the stratified log-rank test to account for tumor site.

The density of CD8+ T cells in each treatment group, at baseline and after treatment, will be visualized using boxplots, and described using summary statistics including means and s.d. presented with 95% confidence intervals. A student t-test or nonparametric Wilcoxon rank-sum test will be used to determine whether the increase in CD8+ T cells is greater in treatment arm B (combination cobimetinib plus atezolizumab) than in treatment arm A (atezolizumab monotherapy).

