13.5.2 Evaluation of Response

All subjects who have completed at least one dose of therapy will be included in the evaluation of response. Each patient will be assigned of the following categories: 1) complete response, 2) partial response, 3) stable disease, 4) progressive disease, 5) early death from malignant disease, 6) early death from toxicity, 7) early death because of other cause, or 9) unknown (not assessable, insufficient data).

The objective response rate is defined as the proportion of response evaluable subjects who have a complete response (CR) or partial response (PR) using RECIST 1.1 criteria at any time during the study. The evaluable population is as defined for the primary

endpoint. Response rates will be reported for each group along with exact confidence intervals, and an exact binomial test will be used to compare response rates across treatment groups.

Evaluation of Correlative Aims

Correlative studies will be performed:

- To measure the baseline expression and on treatment expression of PD-L1 and correlate these variables with treatment response.
- To measure the baseline levels of immune markers including CD8+ T effector cells and CD4+FoxP3+ T regulatory cells, and tumor infiltrating lymphocytes (TILs), major histocompatibility complex (MHC) class I and II expression, and natural killer (NK) cell receptors and ligands expression and correlate these variables with treatment response and toxicity.
- To characterize changes in the immune markers described above after treatment
- To measure changes in circulating immune suppressor cells (MDSC, Treg) in peripheral blood by flow cytometry and test for association with response to therapy.

The overarching aim of these studies is to establish baseline levels for, and measure changes in immunological pathways after treatment. Little is known about baseline levels for these variables in cholangiocarcinoma, let alone changes after treatment, and if the primary and secondary aims are successful, these investigations will establish a biological foundation on which to build in follow up studies.

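### The between-arm tests of ORR and CD8 change omit the tumour-site strata that randomisation, PFS and OS use, which gives up some efficiency and consistency if outcome varies by site

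*Combined protocol and SAP*

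**What the plan says.** Sections 3.4 and 13.3 name one stratification factor with three levels (gallbladder, intrahepatic, extrahepatic): "After the screening phase, eligible subjects will be stratified according to the site of disease". Sections 13.2 and 13.3 add that sample size was worked out without strata because it is unknown whether outcome differs by site.

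The four planned between-arm comparisons of efficacy and of the CD8 biomarker are:

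- PFS (13.1): "using the stratified log-rank test to account for tumor site. An interim analysis will be conducted".
- OS (13.4): "under the assumption of proportional hazards, using the stratified log-rank test to account for tumor site".
- ORR, secondary objective 1.2.2 (13.5.2): "an exact binomial test will be used to compare response rates across treatment groups". No strata, sidedness or alpha are given.
- CD8 change, the main correlative objective (13.4): "A student t-test or nonparametric Wilcoxon rank-sum test will be used to determine whether the increase in CD8+ T cells is greater" in arm B. No strata are given.

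Section 13.1 also says "The analysis will be stratified on site of disease". That sentence stands within the PFS and interim-analysis text and names no endpoint.

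**The concern.** When allocation is stratified, the strata are balanced between arms by design. A test that ignores them then counts between-site variation as noise, although that variation cannot contribute to the difference between arms. If outcome differs by site, the test rejects too rarely under the null and has less power than a stratified test. The plan avoids this for PFS and OS but not for ORR and CD8, and gives no reason for the difference. The stated uncertainty about site is offered as a reason for sizing without strata, not for testing without them. At stake is some power for one secondary and one correlative endpoint, and whether the ORR result is on the same footing as PFS and OS.

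**Working it through.** **1. The plan's own CD8 figure.** Inputs from 13.2: 20 per arm, 0.8 SD, one-sided t-test at 0.05. The noncentrality is 0.8/√(2/20) = 2.53. With 38 degrees of freedom, power is 79.9%. At 1.0 SD it is 92.8%. Both stated figures (80%, more than 90%) reproduce. No ORR power is stated, so there is none to reproduce.

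**2. CD8 if site matters.** Let site explain a share R² of the variance of the change (total SD 1), with sites balanced between arms. R² is an assumption. The arm difference then has variance (1 − R²)(2/20), but the unadjusted t-test estimates it from roughly the full variance. Its true one-sided size is therefore about P(Z > 1.645/√(1 − R²)):

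- R² = 10%: 1.645/0.949 = 1.73, size about 4.2%
- R² = 20%: 1.645/0.894 = 1.84, size about 3.3%
- R² = 30%: 1.645/0.837 = 1.97, size about 2.5%

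Simulation agrees: about 4.1 to 4.3% at 10%, falling to 2.4 to 2.5% at 30%. The site-adjusted model holds about 5%.

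For the adjusted model the noncentrality is 0.8/[√(1 − R²)·√(2/20)] = 2.67, 2.83 and 3.02 on 36 degrees of freedom. Power at 0.8 SD, unadjusted → adjusted:

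| R² | Sites 5/10/5 per arm, exactly balanced | Second simulation |
|---|---|---|
| 0% | 79.8 → 79.8% | 80.3 → 78.5% |
| 10% | 81.2 → 83.5% | 80.2 → 81.7% |
| 20% | 82.8 → 87.6% | 79.4 → 85.5% |
| 30% | 83.6 → 90.7% | 80.1 → 89.0% |

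The gain is 1.5 to 2.3 points at 10%, 4.8 to 6.1 at 20% and 7.1 to 8.9 at 30%.

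**3. ORR.** The documents give 38 evaluable per arm (13.1) and one response rate in this disease, 4/23 or 17%, not split by site (2.3). Everything else is assumed: site mix, response by site, a common odds ratio, and a one-sided 5% level. The planned test is read as Fisher's exact test, because a binomial test does not by itself define a two-arm comparison. With m responders in all, Fisher's p-value is P(X ≥ b), where b is the number of responders in arm B and X is hypergeometric (76 patients, m responders, 38 in arm B). The stratified exact test replaces X by the sum of independent hypergeometric counts, one per site, each given that site's total.

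| Sites per arm | Control ORR by site | Odds ratio | Power, unstratified → stratified | Size, unstratified → stratified |
|---|---|---|---|---|
| 10/18/10 | 10/10/10% | 5 | 80.7 → 80.3% | 1.8 → 1.9% |
| 10/18/10 | 5/10/15% | 5 | 78.6 → 78.9% | 1.7 → 1.9% |
| 10/18/10 | 5/17/30% | 5 | 86.1 → 87.1% | 2.3 → 2.5% |
| 10/18/10 | 2/17/40% | 5 | 79.6 → 83.3% | 2.1 → 2.5% |
| 21/10/7 | 10/10/10% | 4 | 66.3 → 65.9% | not reported |
| 21/10/7 | 5/15/25% | 4 | 60.8 → 63.1% | not reported |
| 21/10/7 | 5/15/25% | 5 | 76.1 → 78.4% | not reported |
| 21/10/7 | 3/15/40% | 4 | 49.0 → 56.8% | 1.4 → 2.3% |
| 21/10/7 | 3/15/40% | 5 | 63.4 → 71.6% | 1.4 → 2.3% |

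The 10/18/10 rows use 20,000 simulated trials and the 21/10/7 rows 8,000, so the simulation error of one power figure is at most √(0.25/8000) = 0.6 point.

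**4. Where the ORR conservatism comes from.** In the 3/15/40% case the pooled control rate is (21×3 + 10×15 + 7×40)/38 = 13%. With that same 13% at every site, Fisher's test already has size 2.3%. Discreteness therefore takes the error from 5% to 2.3%, and ignoring strata takes it from 2.3% to 1.4%, a further 0.9 point. In the 10/18/10 rows the strata account for 0.5 point or less.

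**The case against.** The case for leaving the plan alone is reasonable, and much of it stands.

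- *The plan already stratifies.* The general sentence in 13.1 might be read to cover every endpoint. It sits in the PFS text, and the tests named in 13.4 and 13.5.2 have no strata, so on that reading the sections disagree. The covariate-adjusted logistic models in 13.5.2 relate response to immune markers within each arm and do not compare arms.
- *Dropping strata makes the ORR test conservative.* A reader might infer this as the main cause. It is not: discreteness of the exact test accounts for most of it, and an exact stratified test is still at about 1.9 to 2.5% in the table above.
- *CD8 falls short of its planned power.* A reader might infer this too. The 80% was computed for the unstratified t-test, and unadjusted power stays at about 79 to 84% in every case tried. Adjustment offers extra power; it does not repair a shortfall.
- *The inputs are invented.* This stands. The documents give no site mix, site-specific response or variance share, and the 8-point ORR gain needs response to rise from 3% to 40% across sites. CD8 is a change from baseline, so stable differences between sites partly cancel, and nothing in the documents supports a 20 to 30% variance share.
- *Balance is not assured for CD8.* This stands as well. Paired biopsies are expected in about half of patients, where the tumour is safely accessible, so the balance from randomisation may not carry over. That weakens the conservatism argument for CD8, but it is also a reason to adjust.

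**Conclusion.** The inconsistency is in the text: two of the four comparisons ignore the factor used to randomise. The consequence is small. Under the assumptions shown, stratifying moves ORR power by about -0.5 to +3 points for no to moderate site variation and by about 8 points for an extreme gradient. CD8 power rises by about 1.5 to 2.5 points if site explains 10% of the variance and by 5 to 9 points at 20 to 30%. Ignoring strata adds at most about 1 percentage point to the conservatism of the ORR test in the extreme assumed case. The CD8 t-test also becomes conservative, at about 4.3% down to 2.4% against 5%.

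A reader might go further and infer bias or a raised false-positive rate. The documents do not support that: omitting a balanced factor makes these tests more cautious, not less, and the primary PFS analysis is stratified already. If outcome does not vary by site, there is nothing to gain. This is an optional improvement in efficiency and consistency.

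**What to change.** - **13.5.2:** replace the exact binomial test with an exact Cochran-Mantel-Haenszel test stratified by tumour site, and report the Mantel-Haenszel risk difference with its confidence interval. State the sidedness and alpha in the same sentence.
- **13.4:** compare the change in CD8 density with a linear model containing arm and tumour site, or with a van Elteren site-stratified rank test, and name which one is used. Adjustment also deals with chance site imbalance in the biopsy subset.

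If the sponsor prefers the simple tests, one sentence saying that ORR and CD8 are deliberately unstratified would settle the wording.

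The cost is two sentences. Site is already recorded at randomisation, so no new data are needed. If site turns out to be irrelevant, the price is about half a point of power for ORR and 0 to 2 points for CD8.
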